1.0 Introduction

This Statistical Analysis Plan (SAP) describes the statistical analyses for Study M14-702 "A Phase 3 Study to Evaluate the Safety and Efficacy of Elagolix in Combination with Estradiol/Norethindrone Acetate in Subjects with Moderate to Severe Endometriosis-Associated Pain."

Study M14-702 examines the efficacy and safety of elagolix 200 mg administered twice daily (BID) in combination with estradiol 1 mg/0.5 mg norethindrone acetate (E2/NETA 1 mg/0.5 mg) in subjects with moderate to severe endometriosis associated pain.

The analyses of pharmacokinetic endpoints, pharmacodynamic biomarker endpoints and exploratory research endpoints will not be covered in this SAP.

The SAP will not be updated in case of administrative changes or amendments to the protocol unless the changes impact the analysis.

Unless noted otherwise, all analyses will be performed using SAS Version 9.4 (SAS Institute Inc., Cary, NC 27513) or later under the UNIX operating system.

2.0 Study Design, Objectives and Procedures

2.1 Objectives

The objectives of this study are to:

- Assess the safety and efficacy of elagolix 200 mg administered twice daily (BID) in combination with estradiol 1 mg/0.5 mg norethindrone acetate (E2/NETA 1 mg/0.5 mg) QD compared to placebo at 6 months and 12 months;
- Assess the effect of elagolix 200 mg BID in combination with E2/NETA (1 mg/0.5 mg) QD on bone mineral density (BMD) compared to elagolix 200 mg BID alone at 6 months and compared to placebo at 6 months and 12 months;

- Evaluate the continued safety and efficacy of elagolix 200 mg BID plus E2/NETA (1 mg/0.5 mg) QD for up to 48 months in premenopausal women with moderate to severe endometriosis-associated pain.

2.2 Study Design Overview

[figure not shown]
This Phase 3 study includes a 48-month Treatment Period and is designed to evaluate the safety and efficacy of elagolix in combination with concomitant hormonal add-back therapy (E2/NETA 1 mg/0.5 mg) in the management of endometriosis-associated pain in premenopausal women. The first 12 months of the Treatment Period will employ a randomized, double-blind, placebo-controlled design (12 months), with an elagolix 200 mg BID alone arm (the first 6 months followed by elagolix 200 mg BID plus E2/NETA [1 mg/0.5 mg] QD), and an elagolix 200 mg BID plus E2/NETA (1 mg/0.5 mg) QD arm. The last 36 months of the Treatment Period will be open-label, such that all subjects will receive elagolix 200 mg BID plus E2/NETA (1 mg/0.5 mg) QD.

The total duration for a subject's participation in this study is approximately 51 to 74 months, consisting of the following 4 study periods:

- Washout Period – up to 10 months prior to Screening (only applicable if subject is taking exclusionary medication at the time of consent; duration of washout depends on the type of exclusionary medication being taken).
- Screening Period – approximately 1.5 to 4 months prior to first dose of study drug.
- Treatment Period – up to 48-month treatment duration.
- Follow-Up Period – up to 12 months duration following the last dose of study drug. Subjects are expected to enter Follow-Up after completing Treatment Month 48, or if a subject prematurely discontinues from the Treatment Period at the time of or after Treatment Month 6.

The schematic of the study is shown in [Figure 1](#).

Figure 1. Study Schematic

2.3 Treatment Assignment and Blinding

Approximately 700 subjects will be randomly assigned on Study Day 1 in a 4:1:2 ratio as follows:

- Elagolix plus E2/NETA group: elagolix 200 mg BID plus E2/NETA (1 mg/0.5 mg) QD (n = 400)
- Elagolix alone group: elagolix 200 mg BID (n = 100)
- Placebo group: placebo (n = 200)

Unless otherwise specified, data will be summarized by group as listed above.

2.4 Sample Size Determination

This study plans to enroll approximately 700 subjects, with 400 subjects in the elagolix 200 mg BID plus E2/NETA (1 mg/0.5 mg) QD, 100 subjects in the elagolix 200 mg BID, and 200 subjects in placebo, representing a randomization ratio of 4:1:2. These sample sizes were chosen to ensure a sufficient number of subjects completing 12 months of total treatment with elagolix during the placebo-controlled treatment period for the evaluation of safety assessment. Assuming Non-Menstrual Pelvic Pain (NMPP) responder rates of 54% for the elagolix with E2/NETA therapy dose group and 35% for placebo, and

Dysmenorrhea (DYS) responder rates of 59% for the elagolix with E2/NETA therapy dose group and 23% for placebo, these sample sizes provide greater than 90% power to detect a difference in response rate between elagolix with E2/NETA and placebo for both DYS and NMPP, based on a 2-sided test at the significance level of $\alpha = 0.05$.

2.5 End of 12-Month Placebo-Controlled Treatment Period Analysis

An end-of-placebo-controlled treatment period analysis of the primary, secondary and other efficacy variables along with demographic and safety variables will be performed after the last subject completes the 12-Month placebo-controlled Treatment Period. These analyses will include data collected during the Treatment Period (placebo-controlled and open-label Treatment Periods) and the Follow-Up Period up to the data cut-off for the interim lock. The database will be versioned for an interim soft lock and any discrepant data will be clarified before the versioning. Analyses will be performed by AbbVie.

Since this end-of-placebo-controlled treatment period analysis is the only and final analysis of the primary and key secondary endpoints, no additional adjustment of alpha-level is necessary.

2.6 Treatment Month 24 and Month 36 Analyses

At the end of Treatment Month 24 and Month 36, analysis of the efficacy and safety variables may be performed after the last subject completes the Treatment Month 24 and Month 36 visit, respectively. For subjects who prematurely discontinued during the treatment period, their data collected during the Follow-up Period will be included in the analysis, as appropriate. The database will be versioned for an interim lock and any discrepant data will be clarified before the versioning. Analyses will be performed by AbbVie.

3.0 Endpoints

3.1 Primary Endpoint(s)

The co-primary efficacy endpoints (elagolix plus E2/NETA versus placebo) will be the proportion of responders (defined in Section 3.3.1) at Month 6 based upon the mutually-exclusive scales for daily assessment of Dysmenorrhea (DYS) and Non-Menstrual Pelvic Pain (NMPP) measured by the 4-point Endometriosis Daily Pain Impact Diary. Use of protocol specific rescue analgesic medication for endometriosis-associated pain will also be included in the responder definition.

3.2 Secondary Endpoint(s)

The ranked secondary efficacy endpoints (elagolix plus E2/NETA versus placebo) will be tested in the following order:

1. Change from Baseline to Month 12 in DYS
2. Change from Baseline to Month 6 in DYS
3. Change from Baseline to Month 3 in DYS
4. Change from Baseline to Month 12 in NMPP
5. Change from Baseline to Month 6 in NMPP
6. Change from Baseline to Month 3 in NMPP
7. Change from Baseline to Month 6 in PROMIS Fatigue Short Form 6a T-Score
8. Change from Baseline to Month 12 in dyspareunia
9. Change from Baseline to Month 6 in dyspareunia
10. Change from Baseline to Month 3 in dyspareunia
11. Change from Baseline to Month 12 in PROMIS Fatigue Short Form 6a T-Score
12. Change from Baseline to Month 12 in Overall Endometriosis-Associated Pain
13. Change from Baseline to Month 6 in Overall Endometriosis-Associated Pain

14. Change from Baseline to Month 3 in Overall Endometriosis-Associated Pain

3.3 Other Efficacy Endpoint(s)

The primary and secondary efficacy endpoints are listed in Section 3.1 and Section 3.2, respectively. The additional efficacy endpoints (elagolix plus E2/NETA versus placebo) are:

- Proportion of responders as assessed by change from Baseline in average pain score and rescue analgesic use monthly during the 12-month Placebo-Controlled Treatment Period for DYS, NMPP and dyspareunia, respectively.
- Proportion of responders as assessed by change from Baseline in average pain score alone (i.e., not taking into consideration of rescue analgesic use) monthly during the 12-month Placebo-Controlled Treatment Period for DYS, NMPP and dyspareunia, respectively.
- Change from Baseline in the monthly average pain score (DYS, NMPP, and dyspareunia), as assessed using information from the e-Diary during the 12-month Placebo-Controlled Treatment Period.
- Change from Baseline in rescue analgesic use (average pill counts) to treat endometriosis-related pain, as assessed using information from the e-Diary monthly during the first 12 months of the Treatment Period.
- Proportion of rescue analgesic use responders monthly (based only on reduction of rescue analgesics used) during the first 12 months of the Treatment Period.
- Monthly response in the PGIC and overall endometriosis-associated pain questionnaire during the first 12 months of the Treatment Period.
- Change from baseline for each of six domains of EHP-30 questionnaire scores at each scheduled assessment during the Treatment Period.
- Change from baseline for each category of the EuroQoL-5D (EQ-5D-5L) and index values at each scheduled assessment during the Treatment Period.
- Change from baseline for each measure of the WPAI:SHP at each scheduled assessment during the Treatment Period.

- HCRU at each scheduled assessment during the Treatment Period.
- Change from baseline for the PROMIS Fatigue short Form 6A T-Score at each scheduled assessment during the Treatment Period.

3.4 Safety Endpoint(s)

The safety endpoints will be based on the following evaluations:

- Adverse events Monitoring
- Clinical laboratory tests
- Dual energy X-ray absorptiometry (DXA) scan
- Vital signs
- Endometrial biopsy
- Pelvic ultrasound (transabdominal ultrasound [TAU]/transvaginal ultrasound [TVU])
- Columbia Suicide Severity Rating Scale (C-SSRS)
- Pregnancy
- Uterine bleeding measured by e-Diary

4.0 Analysis Populations

The Full Analysis Set (FAS) is composed of all randomized subjects who have received at least 1 dose of study drug in this study. The data from the FAS will be presented by the treatment group assigned at the time of randomization, even if a subject does not receive the correct treatment or does not follow the protocol until completion. The FAS will be used for all efficacy and baseline analyses unless otherwise specified in the SAP.

Subjects who do not continue into the open-label Treatment Period will be excluded from the analyses in the open-label Treatment Period.

The following populations will be used for safety analyses:

- The Safety Analysis Set includes all randomized subjects who received at least 1 dose of study drug. The data from the Safety Analysis Set will be analyzed based on the actual treatment received at the time of randomization (elagolix plus E2/NETA, elagolix alone or placebo). Subjects who do not continue into the open-label Treatment Period will be excluded from the analyses in the open-label Treatment Period.
- The All Elagolix plus E2/NETA Analysis Set is defined as subjects who received at least 1 dose of elagolix plus E2/NETA in the study (either in the placebo-controlled or open-label Treatment Periods). Subjects will be summarized based on the actual treatment received at the time of randomization (elagolix plus E2/NETA, elagolix alone or placebo).

5.0 Subject Disposition

A summary of subject accountability will be provided where the number of subjects in each of the following categories will be summarized for all randomized subjects by treatment group and overall:

- Subjects randomized in the study.
- Subjects who took at least one dose of study drug.
- Subjects who completed the placebo-controlled Treatment Period.
- Subjects who prematurely discontinued during the placebo-controlled Treatment Period.
- Subjects who entered into the open-label Treatment Period.
- Subjects who prematurely discontinued during the open-label Treatment Period.
- Subjects who completed protocol-specified treatment.
- Subjects who prematurely discontinued study drug (all reasons and primary reason).
- Subjects who entered into the Follow-up Period.

- Subjects who Completed the Follow-up Period.

The number and percentage of subjects who discontinued study drug will be summarized by treatment group and overall as follows based on the Full Analysis Set:

- By any reason for discontinuation
- By primary reason for discontinuation

In addition, the number and percentage of subjects who discontinued study will be summarized for the FAS by treatment group and overall as follows:

- By any reason for discontinuation
- By primary reason for discontinuation

6.0 Study Drug Duration

Duration (days) of treatment will be summarized for the Safety Analysis Set using the number of subjects treated, mean, standard deviation, median, minimum and maximum.

Study drug duration will be summarized as follows:

Placebo-controlled Treatment Period (Safety Analysis Set):

Duration of treatment during the placebo-controlled Treatment Period is defined as follow:

- For subjects who did not continue into the open-label Treatment Period:
 - Last dose date during the placebo-controlled Treatment Period – First dose date during the placebo-controlled Treatment Period + 1
- For subjects who continued into the open-label Treatment Period:
Minimum of
 - Last dose date during the placebo-controlled Treatment Period – First dose date during the placebo-controlled Treatment Period + 1

- First dose date during the open-label Treatment Period – First dose date during the placebo-controlled Treatment Period.

In addition, the number and percentage of subjects in each treatment duration interval (1 – 28 days, > 28 – 56 days, > 56 – 84 days, > 84 – 112 days, > 112 – 140 days, > 140 – 168 days, > 168 days) will be summarized.

Open-label Treatment Period (Safety Analysis Set):

Duration of treatment during the open-label Treatment Period is defined as last dose date during the open-label Treatment Period minus first dose date during the open-label Treatment Period plus 1 day.

In addition, the number and percentage of subjects in each treatment duration interval (1 – 84 days, > 84 – 168 days, > 168 – 252 days, > 252 – 336 days, > 336 – 420 days, > 420 – 504 days, > 504 – 588 days, > 588 – 672 days, > 672 – 756 days, > 756 – 840 days, > 840 – 924 days, > 924 – 1008 days, > 1008 days) will be summarized.

All Elagolix plus E2/NETA Analysis Set:

For subjects who received at least 1 dose of elagolix plus E2/NETA (either in the placebo-controlled or open-label Treatment Periods), the duration of treatment is defined as the last dose date of receiving elagolix plus E2/NETA minus the first dose date of receiving elagolix plus E2/NETA plus 1 day.

In addition, the number and percentage of subjects in each treatment duration interval (1 – 84 days, > 84 – 168 days, > 168 – 252 days, > 252 – 336 days, > 336 – 420 days, > 420 – 504 days, > 504 – 588 days, > 588 – 672 days, > 672 – 756 days, > 756 – 840 days, > 840 – 924 days, > 924 – 1008 days, > 1008 – 1092 days, > 1092 – 1176 days, > 1176 – 1260 days, > 1260 – 1344 days, > 1344 days) will be summarized.

7.0 Demographics, Baseline Characteristics, Medical History, and Prior/Concomitant Medications

Demographics, baseline characteristics, medical history, prior medication, concomitant medication, and post-treatment medication will be summarized by treatment group and overall using the Full Analysis Set. Categorical variables will be summarized with the number and percentage of subjects; percentages will be calculated based on the number of non-missing observations. Continuous variables will be summarized with descriptive statistics (number of non-missing observations, mean and standard deviation, median, minimum and maximum).

7.1 Demographics and Baseline Characteristics

Continuous demographic variables include age, weight, height, and body mass index (BMI). Categorical demographic variables include sex, ethnicity, race, age (18 – 19, 20 – 24, 25 – 29, 30 – 34, 35 – 39, 40 – 44, 45 – 49, ≥ 50 years), BMI (≤ 18.5 , $> 18.5 - < 25$, $\geq 25 - < 30$, $\geq 30 - < 35$, $\geq 35 - < 40$, ≥ 40 kg/m²), tobacco use (current, former, never, unknown), and alcohol use (current, former, never, unknown).

For endometriosis history, the stage of endometriosis at diagnosis as reported by subjects at screening based on their gynecological history will be summarized as the number and percentage of subjects in each category (Stage 1, 2, 3, 4, or unknown) for each treatment group and overall. The number of months between the first study drug dose date and the subject's surgical diagnosis of endometriosis will be summarized for each treatment group and overall.

7.2 Medical History

Medical history and gynecological medical/surgical history data will be coded using the Medical Dictionary for Regulatory Activities (MedDRA). The actual version of the MedDRA coding dictionary will be noted in the statistical tables and clinical study report. The number and percentage of subjects in each medical history category (by MedDRA system organ class and preferred term) will be summarized by treatment group and overall

for the FAS. The system organ class (SOC) will be presented in alphabetical order, and the preferred terms will be presented in alphabetical order within each SOC. Subjects reporting more than one condition/diagnosis will be counted only once in each row (SOC or preferred term).

7.3 Prior, Concomitant, and Post-Treatment Medications

Prior, concomitant, and post-treatment medications will be summarized by generic name for the FAS.

Prior medications are those medications with a start date prior to the first study drug administration date. Prior medications will be summarized separately for prior endometriosis medications and other medications.

Concomitant medications are those medications, other than study drug and protocol specified analgesic medications taken for endometriosis-associated pain which will be recorded in e-Diary during Screening and the first 12 months of Treatment, taken during the Treatment Period with an end date after the first dose of study drug or ongoing at the end of the study, and a start date prior to the last dose of study drug. A medication will be considered a concomitant medication where one of the following three cases occur (1) the start date is missing and the end date is either after or on the first study drug dose date; (2) the start date is not missing and the end date is missing; (3) both the start date and the end date are missing. Concomitant medications will be summarized separately for analgesic medications taken for endometriosis-associated pain recorded in eCRF during the Open-Label Treatment Period and other medications.

Post-treatment medications are those medications with an end date after the last dose of study drug or ongoing at the end of study. Post-treatment medications will be summarized separately for analgesic medications taken for endometriosis-associated pain recorded in eCRF during the Follow-up Period and other medications.

Prior, concomitant, and post-treatment medications will be summarized by ATC Classification and preferred terms from the World Health Organization (WHO) Drug

Dictionary with number and percentage by treatment group and overall. A subject who reports two or more uses of the same medication will be counted only once within each WHO preferred term. A subject with medications with more than one generic name will be counted only once in the overall total.

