5.2.3.2 Concomitant Therapy

All concomitant medications taken during the duration of study participation (Washout [if required], Screening, Treatment, Follow-Up) must be recorded in source documents and eCRFs, along with the reason for use, dates of administration, dosages, routes and frequency.

[figure not shown]
The following concomitant medications are allowed during study participation, as these medications are not expected to significantly confound the efficacy evaluation, nor are there substantial safety concerns with concomitant use:

- Inhaled corticosteroids for treatment of asthma or similar airways diseases
- Over-the-counter and prescription topical, intranasal or local injectable (for occasional use) corticosteroids
- Vaccines
- Triptans or ergotamines for the treatment of infrequent migraine headaches
- Multivitamins
- Anti-depressants
- Non-opioid analgesics (e.g., NSAIDs) may be used for conditions other than endometriosis-associated pain (e.g., acute conditions such as headache or fever)
- Levonorgestrel or ulipristal acetate only when used as emergency contraception (e.g., Plan B)

Given the ongoing COVID-19 pandemic, selected non-live vaccines (e.g., mRNA, non-replicating viral vector, protein subunit, etc.) to prevent SARS-CoV-2 infection may be administered during the Treatment and Post-Treatment Follow-Up Periods, as long as components of the vaccine are not contraindicated.

The decision to receive a locally available vaccine should be based on local guidance and an individual discussion between the treating physician and the subject.

If a subject requires the use of a concomitant medication from a medication class not listed, the AbbVie TA MD should be notified for additional guidance.

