5.2.3.3 Prohibited Therapy

All hormonal forms of birth control (except the emergency contraceptive pill, levonorgestrel 1.5 mg [such as Plan B®], or ulipristal acetate 30 mg [such as Ella® or EllaOne®]) are prohibited during Washout, Screening, Treatment and until the Follow-Up Month 1 visit. Subjects may start hormonal contraception after completion of Follow-Up Month 1, provided that the subject has a documented menstrual period (menses) after the Treatment Period and prior to that visit. For subjects who are prescribed/administered the emergency contraceptive pill during the study, the information should be captured in the source documents and eCRF.

To protect subject safety and to minimize confounding the study results, the following concomitant medications are prohibited during the study as specified below:

[figure not shown]

Table 2. Prohibited Medications

Prohibited During the Washout, Screening, Treatment, and Follow-Up Periods			
GnRH agonist	Leuprolide acetate (Lupron®)		
Prohibited During the Washout, Screening and Treatment Periods and thru Follow-Up Month 1			
Hormonal Medications and Non-hormonal Estrogen Supplements, such as:	GnRH agonist: nafarelin acetate (Synarel®), goserelin acetate (Zoladex®) Danazol (Danocrine®, Cyclomen®) Medroxyprogesterone Acetate (Depo-Provera®, Provera®) Oral contraceptives Other progestins (oral, vaginal, IUDs, implantable) Levonorgestrel (except emergency contraception, i.e., levonorgestrel 1.5 mg) Spironolactone Mifepristone Ulipristal acetate (except emergency contraception, i.e., ulipristal acetate 30 mg) Testosterone preparations Tamoxifen Bromocriptine (Parlodel®) Cabergoline (Dostinex®) Raloxifene (Evista®, Optruma, or generics) Bazedoxifene (Conbriza) Aromatase Inhibitors (e.g., Anastrozole [Arimidex®], Exemestane [Aromasin®]) Natural Estrogen preparations or herbal remedies/supplements to treat premenstrual or gynecological problems (e.g., soy-containing supplements, black cohosh)		

[figure not shown]

Table 2. Prohibited Medications (Continued)

Prohibited During the Screening and Treatment Periods			
Immediate Release (IR) Opioid Analgesics, such as:	Oxymorphone Hydromorphone Morphine Buprenorphine Except for short-term use as noted below.		
Long-acting, Controlled Release (CR), Extended Release (ER) or Transdermal Opioid Analgesics, such as:	CR/ER Morphine CR/ER Hydromorphone CR/ER Oxymorphone CR/ER Oxycodone ER Tapentadol ER Tramadol Fentanyl Methadone Levorphanol Buprenorphine		

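### SAP 7.3: missing-date case (2) has no start-date limit, so it conflicts with the definition beside it for drugs started on or after the last dose with no end date

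*SAP*

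**What the plan says.** SAP 7.3 has three relevant parts.

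- **Base definition of concomitant medication.** Apart from study drug and diary-recorded rescue analgesics, it covers drugs "taken during the Treatment Period with an end date after the first dose of study drug". The same sentence then adds an alternative to that end-date condition, and a limit on when the drug began: "or ongoing at the end of the study, and a start date prior to the last dose of study drug". An ongoing drug is thus already included, provided it began before the last dose.
- **Missing-date cases.** The next sentence begins "A medication will be considered a concomitant medication where one of the following three cases occur". Case (1) is a missing start date with an end date on or after the first dose date. Case (2) is "2) the start date is not missing and the end date is missing". Case (3) is both dates missing.
- **Post-treatment definition.** "Post-treatment medications are those medications with an end date after the last dose of study drug or ongoing at the end of study".

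On data collection, Protocol 5.2.3.2 says "All concomitant medications taken during the duration of study participation (Washout [if required], Screening, Treatment, Follow-Up) must be recorded in source documents and eCRFs", and the Follow-Up table in Protocol Appendix C schedules medication review at Months 1, 6 and 12. Protocol 5.2.3.3 bars hormonal contraception, except emergency contraception, through treatment and up to the Follow-Up Month 1 visit. It then says "Subjects may start hormonal contraception after completion of Follow-Up Month 1", subject to a documented menses.

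**The concern.** The base definition limits the start date and case (2) does not. The cases are worded as sufficient on their own, and the SAP does not say which sentence governs when they disagree. A programmer who codes the three cases as written would class a drug first taken in Follow-Up, with no end date, as taken with study drug.

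What is at stake is how the concomitant-medication table reads. Hormonal contraceptives are barred on treatment and allowed later, so a Follow-Up start shown there would look like prohibited use. The same applies to drugs that Protocol Table 2 bars through the Treatment Period but not in Follow-Up, such as several opioids and CYP3A inducers. The table is presented by treatment group, so any such entries would appear against an arm.

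**Working it through.** No figure in the plan bears on this point and no arithmetic applies. The check applies each sentence of SAP 7.3 to the same records.

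| Record | Base definition | Case (2), literal | Post-treatment definition |
|---|---|---|---|
| A: started on or after last dose, no end date | Not concomitant | Concomitant | Yes, if ongoing |
| B: started before last dose, no end date, ongoing | Concomitant | Concomitant | Yes |
| C: started after last dose, end date known | Not concomitant | Does not apply | Yes |

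Only record A produces a conflict. Record B properly belongs in both tables, because use spans the last dose. Record C is classified correctly.

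**Can record A occur?** Yes. Follow-Up medications go into the eCRF (Protocol 5.2.3.2), and hormonal contraception may begin in Follow-Up (Protocol 5.2.3.3). It can also occur at the first lock. SAP 2.5 includes Follow-Up data up to the cut-off, and women who stop at or after Month 6 are expected to enter Follow-Up (Protocol 5.4.1).

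**Do the cases inherit the limits of the base definition?** The text does not say. Case (1) suggests they may not, because it states its own end-date bound. That bound would be redundant if the base limits carried over, and it differs slightly: on or after the first dose date, against after the first dose in the definition. If the cases set their own bounds, case (2) has none.

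**Effect of adding the limit.** If case (2) also required a start before the last dose, record A would fail both concomitant tests and remain post-treatment. Records B and C would not change.

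**The case against.** The best defence is that the three cases are conventions for absent dates, to be applied inside the definition they follow. In case (2) only the end date is absent. The start date is known, so the test "and a start date prior to the last dose of study drug" can still be applied, and a Follow-Up start fails it. This is a sensible reading and probably the intended one, so misclassification is not certain. It does not remove the problem, because the cases are worded as sufficient and case (1) carries its own bound.

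A second defence is that SAP 7.3 treats ongoing and missing as different terms. If the database stores an ongoing flag separately from a missing end date, a contraceptive marked ongoing falls under the base definition, which excludes it, and case (2) may not be triggered. The documents do not settle this. It could reduce the affected records, possibly to none, but the two sentences would still conflict.

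A reader might infer three stronger things that the documents do not support.

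- **That many women will be wrongly shown with on-treatment hormonal use.** The documents do not give the number entering Follow-Up, the share starting a hormonal method, or the share with no end date. A count would be assumption throughout.
- **That the bone recovery results are affected.** The Follow-Up analyses and recovery statistic in SAP 9.5.2.2 do not use the medication classification.
- **That post-treatment exposure is hidden.** An ongoing Follow-Up drug still meets the post-treatment definition, so for it the worst outcome is a double listing. Start dates are recorded (Protocol 5.2.3), and protocol deviations are summarized separately (Protocol 8.1.3), so a false entry can be traced.

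**Conclusion.** The point holds in a narrow form: wrong as written, and minor. Two adjacent sentences of SAP 7.3 give opposite answers for a drug started on or after the last dose with no end date. Read literally, case (2) gives the wrong one.

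The effect is confined to descriptive medication tables, where it could create a false appearance of prohibited on-treatment use. The co-primary, ranked secondary and bone mineral density analyses do not depend on it. The number of affected records cannot be derived from the documents.

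The conclusion that the sentences conflict rests on the text alone. Whether any table entry is actually wrong depends on two things the SAP leaves open: whether the cases are programmed as sufficient on their own, and whether ongoing drugs are held with a missing end date.

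**What to change.** Reword case (2) so that it requires three things: a known start date, that date falling before the last dose of study drug, and a missing end date. Use the base definition's own limit (before the last dose). A limit of on or before would create a new mismatch for drugs started on the day of the last dose.

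Drugs started after the last dose would then appear only in the post-treatment table. That definition has no missing-date rule of its own. A few words could confirm that a drug with a known start after the last dose counts as post-treatment even if its end date is missing and it is not marked ongoing.

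The cost is one clause in the SAP and the matching line of table programming. No data collection changes, and correctly classified records keep their place.
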